## **2. GENERAL ANALYSIS DEFINITIONS**

### **2.1. Study Phases**

A baseline (or reference) value for safety and immunogenicity will be defined as the value of the last available assessment prior to the first vaccination on Day 1. If there was no immunogenicity assessment done pre-vaccination, the assessment post-vaccination on Day 1 can be used as the baseline value for the immunogenicity analysis, if available.

A baseline (or reference) value for the efficacy analysis of the first RSV season will be defined as the worst value of the available assessment at Day 1 visit, if Day 1 visit is not available the Day 1 unscheduled visit closest to the day of vaccination will be used. In case two or more assessments are available at the same visit or at the same day of the selected baseline visit (for example assessments both at the eDiary and eDevice) the worst will be used (per question).

A new baseline (or reference) value for the efficacy analysis of the second and third RSV season will be defined as the worst value of the available assessment at Day 365/Day 730 visit, if Day 365/Day 730 visit is not available the Day 365/Day 730 unscheduled visit closest to the relative day 365/day 730 will be used. In case no Day 365/Day 730 visit (schedule or unscheduled) is available then the baseline of the first/second (or first) RSV season will be used. In case two or more assessments are available at the same visit or at the same day of the selected baseline visit (for example assessments both at the eDiary and eDevice) the worst value will be used (per question).

The safety analysis will present all results by period, unless specified otherwise. Immunogenicity results will be presented per analysis time point (see Section 2.1.2) as appropriate. Listings will be shown per phase, period and time point. Efficacy results will be presented across the entire season or per timepoint, where appropriate.

Study day or relative day is defined as follows:

Study Day = visit date - date of Day 1 + 1; if visit date > date of Day 1 (date of first vaccination).

Study Day = visit date - date of Day 1; if visit date < date of Day 1 (date of first vaccination).

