**Table 6: Case Definitions**

Case Definition #1	Case Definition #2	Case Definition #3
≥3 symptoms of LRTI (new onset or worsening)	≥2 symptoms of LRTI (new onset or worsening)	≥2 symptoms of LRTI, OR ≥1 symptom of LRTI combined with ≥1 systemic symptom (new onset or worsening)
RT-PCR confirmation of RSV		

LRTI = lower respiratory tract infection

To meet the primary endpoint criteria for a case definition, the following criteria need to be fulfilled:

a <https://www.cdc.gov/surveillance/nrevss/rsv/region.html>

- The participant must show the necessary number of signs and symptoms (new onset or worsening) according to the considered case definition. Which symptoms will be taken into account and how the number of symptoms will be counted is defined in Section 4.4.2.1.1.
- The considered ARI episode must be RT-PCR confirmed for RSV. RSV RT-PCR confirmation is defined in Section 4.4.2.1.2.

First occurrence of a considered endpoint is defined as the first day of symptoms of the first RSV-confirmed ARI episode where the criteria for the respective case definition are fulfilled on at least one assessment of the considered episode. Only episodes occurring in the first season of the participant are taken into account for the primary analysis.

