#### **New onset or worsening of symptoms:**

To determine new onset or worsening of symptoms, symptoms should be compared with the respective baseline of the season wherein the episode started:

- Clinical assessment by the site staff will be compared with clinical assessment baseline by the site staff.
- Patient reported outcomes reported on the site's eDevice and on the participants eDiary will be compared with the baseline patient reported outcomes.

Symptoms present during an ARI episode but not at the baseline assessment will be considered as symptoms with a new onset. Symptoms present at the baseline assessment that become worse (higher severity) during the ARI episode will be considered as worsening symptoms.

For assessments that are numerically scored (Decreased oxygen, tachypnea, and fever) new onset or worsening is defined as follows:

- Decreased oxygen saturation is defined as:
  - oxygen saturation of  $<90\%$  for participants with a baseline oxygen saturation of  $\geq 90\%$  or a missing baseline at randomization (new onset)
  - for participants with baseline oxygen saturation  $<90\%$ , decreased oxygen saturation is defined as a  $\geq 3\%$  decrease in their oxygen saturation from baseline (worsening).
- Tachypnea is defined by respiratory rate (RR)  $>20$  breaths per minute:
  - For subjects with baseline RR  $\leq 20$  or a missing baseline, a value  $>20$  is considered a new onset.
  - For subjects with baseline RR  $>20$  (and  $\leq 25$ ), a value  $>25$  is considered a worsening.
- Fever: all temperatures  $>37.8^{\circ}\text{C}$  during an ARI episode will be considered as a fever, regardless of the baseline temperature of the participant. For example, if a subject has baseline temperature of 37.9 degrees Celsius and during the ARI episode his temperature of is again 37.9 degrees Celsius, it will be counted as a systemic symptom of fever.

Note 1: Shortness of breath and respiratory effort reported at the clinical assessment form will not be taken into account for the case definitions.

Note 2: If a participant at the clinical assessment reported a new onset or worsening of dyspnea and had decreased oxygen saturation, then it counts only as one symptom towards the case definitions. Similarly, if a participant had a new onset or worsening of wheezing and rhonchi, rales or other sign of consolidation, it also counts as one symptom.

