Note 3: Example of selecting the baseline of the season in which the ARI started: if an ARI episode starts in Season 2 and continues during Season 3, then all assessments related to that ARI episode will be evaluated in comparison to the Day 365 baseline to determine new onset or worsening.

Missing baseline assessments will not be imputed, in case of missing baseline symptoms the participant will be considered to have no baseline symptoms at all.

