#### **4.4.2.1.3. ARI Episode Duration**

The duration of an ARI episode is defined as: *Last day of symptoms above baseline - start date of ARI + 1*. The ARI Day 1 and ARI Day 3-5 visits are always taken into account for the duration if there is a new onset or worsening of a symptom. The ARI Day 29 is taken into account for the duration only if the RiiQ assessments reported by the participants on his/her home device go up to or exceed the ARI Day 29 visit date (actual date). In this case, ARI Day 29 site assessments occurring after this last RiiQ assessment reported by the participants on his/her home device (actual day) are not taken into account for the duration. End of Season as well as Day 365 and Day 730 visits are excluded when determining ARI end dates. Only URTI and LRTI symptoms from clinical assessment and patient reported outcome will be used in calculating the duration of an ARI episode (Table 8).

Moreover, for ARIs with no new onset or worsening of symptoms, duration will not be calculated.

For calculating the ARI duration, the following rules may be used:

- For all ARIs the start dates are reported in the CRF (=CE.CESTDTC where CETERM=ACUTE RESPIRATORY INFECTION and CE.CECAT= ‘’).

- Then a temporary end date for each ARI is created:
  - In case a participant has multiple ARIs, the temporary end date is set as a day before the start of the next ARI.
  - In case a participant has only one ARI, the temporary end date is set as the day of database cut off (15 May 2020).
- Search between the ARI start date and the temporary end date, for the last date the participant had a new onset or worsening of URTI or LRTI symptoms (Table 8), at the RiiQ assessments completed on his /her device and set it as ‘*enddate1*’.
- If the RiiQ assessments, between the ARI start date and the temporary end date, reported by the participants on his/her home device do not reach the actual ARI Day 29 visit date. Search between the ‘ARI Day 1’ and ‘ARI Day 3-5’ visits (both scheduled and unscheduled), for the last date the participant had a new onset or worsening of URTI or LRTI symptoms (Table 8), at the assessments collected during these visits and set it as ‘*enddate2*’.

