### 5.4. Efficacy Analysis

#### 5.4.1. Exploratory Efficacy Variable(s)

##### 5.4.1.1. Definition

Other exploratory efficacy endpoints are:

- **First occurrence of RT-PCR-confirmed RSV-mediated LRTD during the second RSV season and during the third RSV season according to Case Definition 1**

This is defined similarly as the primary endpoint, but only counted in the respective RSV season. The baseline assessment for the second RSV season is the Day 365 (Month 12) visit and for the third RSV season it is the Day 730 (Month 24) visit (see Section 2.1). New onset or worsening is defined similarly as for the primary endpoint, by comparing symptoms occurring during the ARI episode to symptoms reported at the new baseline (instead of by comparing to Day 1). First occurrence of a considered endpoint during the second or third RSV season is defined as the first episode of the considered endpoint in a given RSV season (regardless A or B strain, unless otherwise specified).

- **First occurrence of RT-PCR-confirmed RSV-mediated LRTD over season two and three and over all three RSV seasons according Case Definition 1**

This is defined similarly as the primary endpoint but taking into account events over season two and three and over all three seasons. The baseline assessment for the second RSV season is the Day 365 (Month 12) visit and for the third RSV season it is the Day 730 (Month 24) visit (see Section 2.1). New onset or worsening is defined similarly as for the primary endpoint, by comparing symptoms occurring during the ARI episode to symptoms reported at the new baseline (instead of comparing to Day 1). When evaluating the vaccine efficacy over season two and three or over all three seasons, first occurrence of a considered endpoint over two or three seasons is defined as the first episode over the two or three periods (regardless A or B strain, unless otherwise specified).

The following exploratory efficacy endpoints, are defined similarly as the corresponding endpoints during the first RSV season (see Section 4.4.3 and 4.4.4), but baseline, new onset or worsening and first occurrence are defined the same way as for RT-PCR-confirmed RSV-mediated LRTD, during the second and third RSV season and over season two and three or over all three RSV seasons. These endpoints might also be explored during the second or third RSV season and across season two and three or across all three RSV seasons.

- **First occurrence of any RT-PCR-confirmed RSV ARI**

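### The Season 2 and 3 symptom baseline may be recorded during an acute respiratory infection, so later episodes in that season can fail Case Definition 1; the expected loss is small and confined to exploratory analyses

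*SAP*

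**What the plan says.** Section 2.1 sets a new efficacy baseline for the second and third seasons, "defined as the worst value of the available assessment at Day 365/Day 730 visit". Where several assessments exist on the same day, for example eDiary and eDevice, the worst answer to each question is taken. An earlier baseline comes in only when there is no scheduled or unscheduled Day 365/Day 730 visit; "then the baseline of the first/second (or first) RSV season will be used" covers that case alone.

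Section 5.4.1.1 judges the Season 2 and 3 endpoints "by comparing symptoms occurring during the ARI episode to symptoms reported at the new baseline". Section 4.4.2.1.1 adds that "Symptoms present at the baseline assessment that become worse (higher severity) during the ARI episode will be considered as worsening symptoms", so a symptom already present at baseline counts only if its severity rises. Case Definition 1 (Table 6) requires three or more such lower respiratory symptoms, all on one assessment.

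The SAP expects illness to cross these visits. Note 3 in Section 4.4.2.1.1 uses the example "if an ARI episode starts in Season 2 and continues during Season 3" and keeps the earlier baseline for that episode. Section 2.3.3 assigns such an episode's data to the earlier year. Section 4.4.2.1.3 states that "End of Season as well as Day 365 and Day 730 visits are excluded when determining ARI end dates".

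**The concern.** Each of the provisions for a straddling ARI deals with that episode only. None stops its symptoms, recorded at the Day 365 or Day 730 visit, from becoming the reference for every later episode in the new season. Taking the worst value per question raises that reference further.

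Onset on the visit day is also exposed. Table 2 ends the previous follow-up year on the day before the visit, and Section 5.4.1.2 starts the season's follow-up at the visit. An ARI starting that day therefore belongs to the new season and is compared with symptoms of the same illness.

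At stake are Case Definition 1 in Season 2, in Season 3 and over Seasons 2 and 3, and the Season 2 and 3 part of the three-season endpoint. Case Definition 1 is the only LRTD definition retained for these analyses (Section 1.6), and Section 5 warns that cases may be few. Change scores and AUCs measured from Day 365/Day 730 (Sections 5.5 and 5.7) are pulled downward for the same participants.

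**Working it through.** The SAP states no figure that rests on this rule. The steps below apply the rule and then size it.

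**1. Loss of Case Definition 1 on the diary, given symptoms at baseline.** The RiiQ has four lower respiratory symptoms (Table 7), each scored 0–3 (Section 4.5.1). From a symptom-free baseline, the profiles with at least three scores above zero number 3⁴ + 4 × 3³ = 81 + 108 = 189. Counting only scores above baseline, and weighting profiles equally (an assumption):

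| Baseline symptoms | Profiles still qualifying | Share lost |
|---|---|---|
| one mild | 162 | 14% |
| two mild | 132 | 30% |
| two moderate | 69 | 63% |
| three moderate | 31 | 84% |
| four moderate | 13 | 93% |
| two severe | 0 | 100% |

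Example: an RSV episode with cough 2, wheeze 2, shortness of breath 2 and sputum 1 scores four symptoms against a clean baseline. If cough 2 and wheeze 2 were recorded at the visit, it scores two and fails on the diary. The range 30%–90% is carried forward.

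**2. Participants ill at the visit.** Assumed: 0.5–1.0 ARI per person-year, lasting 10–21 days.
- Low: 0.5 × 10/365 = 1.4%.
- High: 1.0 × 21/365 = 5.8%.
- In an assumed 5,000 participants: about 70 to 290.

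For context, 5,800 less Subcohorts A (240) and B (270) leaves 5,290 before dropout.

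**3. Event rate.** Table 4 assumes 0.75% incidence and 70% efficacy, and expects 9 events from 2,000 added participants. With 900 evaluable per arm (Section 4.4.1.1.1), 900 × 0.0075 + 900 × 0.00225 = 6.75 + 2.03 = 8.8. This reproduces the 9 and shows that 0.75% is the placebo rate. The average over arms is (0.75% + 0.225%)/2 = 0.49%. It refers to Case Definition 2, so the rate for Case Definition 1 is no higher.

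**4. Events lost per season, both arms.**
- Low: 70 × 0.0049 × 0.3 = 0.1.
- High: 290 × 0.0049 × 0.9 = 1.3.

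As a share of events this is 1.4% × 0.3 = 0.4% to 5.8% × 0.9 = 5.2%. The calculation assumes that RSV risk is the same whether or not a participant was ill at the visit, gives no credit for cases met through the clinical assessment, and does not count visit-day onsets separately.

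**5. Vaccine efficacy.** With true efficacy 70%, observed efficacy is 1 − 0.3 × (1 − loss in vaccine)/(1 − loss in placebo).
- Equal loss: 70%.
- Assumed 9% loss in placebo and 3% in vaccine: 1 − 0.3 × 0.97/0.91 = 68%.
- The reverse: 1 − 0.3 × 0.91/0.97 = 72%.

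**The case against.** The strongest objection is that the effect is too small to matter. The affected endpoints are exploratory, may be reduced to listings if cases are few (Section 5), and on the figures above lose about one event per season at most. That stands, and it limits the weight of the point.

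Three further objections also stand in part.
- Any RSV ARI needs only one new or worse upper or lower respiratory symptom (Section 4.4.3.1), so it is much less exposed than Case Definition 1.
- Case Definition 1 can also be met on the clinical assessment, which has its own baseline and adds tachypnea. That baseline comes from the same visit under the same rule, so the protection is partial.
- The protocol, not shown here, may say how visits are handled when a participant is ill. The SAP does not rely on any such rule, and Section 2.3.3 and Note 3 presume that ARIs do span the boundary.

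A reader might infer from the 70–290 figure that cases are lost on that scale. It counts people with an affected baseline under assumed rates. A case is lost only if one of them later has a qualifying RSV episode that season and it fails the worsening test.

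**Conclusion.** The gap is real. As written, Section 2.1 lets illness symptoms serve as the Season 2 or 3 baseline, and some genuine episodes would then fail Case Definition 1. The size, about 0.1–1.3 events per season across both arms, rests on assumed ARI rates, durations, cohort size and equally weighted symptom profiles, combined with the SAP's own incidence and efficacy assumptions.

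Two stronger readings are not supported. One is that the durability estimates are biased: equal loss in both arms leaves efficacy unchanged and costs only events and precision, unequal loss could move it slightly either way, and the SAP gives no basis for assuming inequality. The other is that the whole three-season result or the primary analysis is compromised: Season 1 events are judged against the Day 1 baseline and are untouched. The change is still worth making because it is cheap and extends a fallback the SAP already has.

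**What to change.** Add to Section 2.1: *A Day 365/Day 730 assessment made on or after the CRF onset date of an ARI (including onset on the visit day) and up to its end date under Section 4.4.2.1.3 is not used as the efficacy baseline; the previous season's baseline is used. Where the end date is missing under Section 4.4.2.1.3, only an assessment on the onset day is excluded.* Apply it to the case definitions, any RSV ARI, the clinical assessment and the patient-reported change scores for Seasons 2 and 3.

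Report by arm how many baselines are affected, and give the Case Definition 1 result under the present Section 2.1 rule as a sensitivity analysis.

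State the limits of the flag. Section 1.2 lists no ARI surveillance between Seasons 1 and 2, and Section 5.14 puts the end of first-season surveillance at 20 March 2020. At Day 365 the flag will therefore capture mainly visit-day onset, and it works better at Day 730. Because Day 365/Day 730 visits do not count toward ARI end dates, an illness whose diary entries stopped before the visit would also go unflagged.

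The cost is a short addition to Section 2.1 and a programming flag, with no new data. The downside is that a few participants keep a baseline a year older, so chronic symptoms acquired since then could count as new onset; the sensitivity analysis shows whether that matters.

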### 2.1.1. Phase Definitions

The phases in the study will be constructed as outlined in Table 2 for all participants, excluding revaccination periods:

**Table 2: Phase Definitions all subjects (excluding revaccination periods)**

Phase	Phase #	Period	Period #	Interval	
				From	To
Screening	1			Date and time of signing the informed consent form	One minute prior to start of post dose 1 period
Regimen	2	Post-dose	1	Date and time of first vaccination	Minimum of: 
 
a) 23:59 at the date of last contact (for early discontinuation from study)
 
b) 23:59 at the date of database cut-off date
 
c) Maximum (28 days after first vaccination at 23:59, scheduled visit 4 weeks after first vaccination at 23:59)
 

**Table 2: Phase Definitions all subjects (excluding revaccination periods)**

Phase	Phase #	Period	Period #	Interval	
				From	To
First Year Follow up	3			One minute after Post-dose period end	Minimum of: a) 23:59 at the date of last contact (for early discontinuation from study) b) 23:59 at the date of database cut-off date c) 23:59 at the day before the Day 365 visit** (for participants not in Revaccination Subcohort A) d) One minute prior to the revaccination (for Revaccination Subcohort A)
Second Year Follow up	4			One minute after: a) post-revaccination period for participants in Revaccination Subcohort A b) first year follow up phase for the remaining participants	Minimum of: a) 23:59 at the Date of last contact (for early discontinuation or participants that completed the study (Revaccination Subcohort A)) b) 23:59 at the date of database cut-off date (in case of interim) c) 23:59 at the day before the Day 730 visit** (for participants in Revaccination Subcohorts C and D and for ongoing participants in Cohort 1) d) One minute prior to the revaccination (for Revaccination Subcohorts B and 2A)
Third Year Follow up	5			One minute after: a) post-revaccination for participants in Revaccinat	Minimum of: a) 23:59 at the Date of last contact (for early discontinuation or participants that completed the study (Cohort 1 and Revaccination Subcohorts

**Table 2: Phase Definitions all subjects (excluding revaccination periods)**

Phase	Phase #	Period	Period #	Interval	
				From	To
				ion Subcohorts B and 2A b) Second year follow-up for the remaining participants (except Revaccination Subcohort 1A)	1B and 2A)) b) 23:59 at the date of database cut-off date (in case of interim) c) 23:59 at Day 1 Vaccination + 1094 (for participants in Revaccination Subcohort D) d) One minute prior to the revaccination (for Revaccination Subcohort C and 2B)
Fourth Year Follow up	6			One minute after: a) post-revaccination for participants in Revaccination Subcohorts C and 2B b) Third year follow-up for the participants in Revaccination Subcohort D	Minimum of: a) 23:59 at the Date of last contact (for early discontinuation or participants that completed the study (Participants in Revaccination Subcohorts 2B and C) b) 23:59 at the date of database cut-off date (in case of interim) c) One minute prior to the revaccination (for Revaccination Subcohort D)
Fifth Year Follow up	7			One minute after: a) post-revaccination for participants in Revaccination Subcohort D	Minimum of: a) 23:59 at the Date of last contact (for early discontinuation or participants that completed the study (Revaccination Subcohort D) b) 23:59 at the date of database cut-off date

Additional phases will be applicable for the participants in the Revaccination Cohorts (Table 3):

**Table 3: Phase Definitions from revaccination onwards**

Phase	Phase #	Period	Period #	Interval	
				From	To
Regimen	8	Post-Revaccination 1 +	2	Date and time of second vaccination	Minimum of: a) 23:59 at the date of last contact (for early discontinuation from study) b) 23:59 at the date of database cut-off date c) Maximum (28 days after second vaccination at 23:59, scheduled visit 4 weeks after second vaccination at 23:59)
Regimen	9	Post-Revaccination 2 ++	3	Date and time of third vaccination	Minimum of: a) 23:59 at the date of last contact (for early discontinuation from study) b) 23:59 at the date of database cut-off date c) Maximum (28 days after third vaccination at 23:59, scheduled visit 4 weeks after third vaccination at 23:59)

The combination of 'Post dose' period and 'First Year follow up' period will be referred as 'Year One'. The combination of a 'Post-Revaccination' period and 'XXX Year Follow up' period will be referred as 'Year XXX'. The combination of multiple years will be referred as the 'Overall' phase.

\* time refers to hours and minutes

\*\* If Day 365/730/1095/1460/1628 is missing, then the relative day 365/730/1095/1460/1628 will be used to define the end of the 'First/Second/Third/Fourth/Fifth Year follow up' period. For Day 365/Day 730 this will only be done given that there are ARI surveillance questions available after this relative day to avoid creating artificial follow-up phases when there were actually none present.

+Only participants that are part of the Revaccination Subcohorts will have a post-revaccination period.

++Only participants that are part of the Revaccination Subcohorts 2A and 2B will have a third vaccination, and thus will have a second post-revaccination period.

